5.8. Infusion-Related Reactions

5.8.1. Guidance for Management of Infusion-Related Reactions

All subjects will be monitored for infusion-related reactions (IRR) or injection-related reactions during the infusion and immediately afterwards for at least 60 minutes post infusion for the first 2 infusions, and at least 30 minutes for subsequent infusions. Injection-related reactions can be localized at the site of the injection or systemic and should be treated per institutional guidelines. Acute IRRs typically occur within 24 hours of infusion and may manifest as erythema, pruritis, fever, or chills and progress to an anaphylactic-type reaction. Clinical sites should be prepared to manage any acute hypersensitivity or hypersensitivity-like events. [Table 1](#) provides guidelines on management of acute infusion reactions as well as management of subsequent AL001 dosing.

In addition, in the event of an IRR, blood samples should be obtained for serum PK and ADA assessments of AL001 or placebo, and blood samples should be drawn for assessment by the laboratory: C-reactive protein (CRP), ferritin, tryptase, and IL-6 (at 1 to 2 hours after the IRR, then again at 48-72 hours after the IRR). Where possible, clinical laboratory samples should be drawn at the site for central laboratory; however, local laboratories may be utilized, and results assessed for safety by the investigator.

Further details regarding IRRs are provided in the Investigator Brochure.

Table 1: Guidelines for Management of Acute Infusion-Related Reactions

WHO Toxicity Criteria	Treatment	Pre-Medication at Subsequent Dosing
Grade 1 Mild transient reaction; infusion interruption not indicated; intervention not indicated	Stop infusion and monitor symptoms. If symptoms resolve without intervention, the infusion may be restarted at 50% of the original infusion rate.	None

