Grade 2 Therapy or infusion interruption indicated but responds promptly to symptomatic treatment (eg, antihistamines, NSAIDs, narcotics, IV fluids); prophylactic medications indicated for ≤ 24 hours	
Stop infusion and monitor symptoms. Additional appropriate medical therapy may include but is not limited to IV fluids, antihistamines, and antipyretics. Increase monitoring of vital signs as medically indicated until the participant is deemed medically stable in the opinion of the investigator.
 
If symptoms resolve following supportive treatment, the infusion may be restarted at 50% of the original infusion rate. Otherwise, dosing will be held until symptoms resolve and the participant should be premedicated for the next scheduled dose.
 
Subjects who develop Grade 2 toxicity despite adequate pre-medication and infusion rate reduction should be permanently discontinued from further trial treatment administration.
	Subject should be premedicated prior to next dose of study drug with antihistamine (eg, diphenhydramine 50 mg po) and antipyretic (eg, acetaminophen / paracetamol 500-1000 mg po).

Grades 3 or 4
 
Grade 3: Prolonged (eg, not rapidly responsive to symptomatic medication and/or interruption of infusion); recurrence of symptoms following initial improvement; hospitalization indicated for clinical sequelae
 
Grade 4: Life-threatening consequences; urgent intervention indicated
	
Stop infusion and increase monitoring of vital signs as medically indicated. Additional appropriate medical therapy may include but is not limited to IV fluids, IV steroids (eg, hydrocortisone 100-200 mg or corticosteroid equivalent), IV antihistamines, vasopressors, and antipyretics. Hospitalization may be indicated.
 
Subjects with signs or symptoms that may be consistent with cardiac etiology should be assessed by ECGs, cardiac enzymes (eg, creatinine-MB isoenzyme, troponins, brain natriuretic peptide) to rule out myocardial infarction, and echocardiogram should be performed unless cardiac failure is ruled out by preceding investigations.
 
Subject is permanently discontinued from further trial treatment administration.
	Any subject with a serious Grade 3 or any Grade 4 event will not be permitted to re-dose. Any subsequent redosing of nonserious Grade 3 events must be discussed and approved with the Medical Monitor.

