6. STUDY DRUG DISCONTINUATION AND SUBJECT WITHDRAWAL FROM THE STUDY

6.1. Study Drug Discontinuation

An investigator may discontinue study drug or a subject may also choose to discontinue study drug at any time. Subjects who plan to discontinue early from the study drug or study should complete an Early Termination Visit 8 weeks after the last dose of study treatment.

The following is a list of possible reasons for study drug discontinuation:

1. Subject is noncompliant with the protocol
2. Subject is lost to follow-up
3. Subject withdraws consent
4. Subject has a serious or intolerable AE that, in the opinion of the investigator, requires withdrawal from the study treatment
5. Occurrence of an intercurrent illness that, in the opinion of the investigator, will affect assessments of clinical status or safety to a significant degree
6. Use of a nonpermitted concomitant medication
7. Pregnancy
8. Discretion of the investigator and Medical Monitor
9. Serum transaminases (ALT or AST) $>3 \times$ ULN and total bilirubin $>2 \times$ ULN without an alternative explanation
10. Anaphylaxis
11. Infusion-related or injection-related reaction despite adequate pre-medication for an initial occurrence of a moderate to severe infusion related reaction or if the subject experiences any of the following events: mucosal tissue involvement, airway compromise, or symptomatic hypotension with systolic BP <90 mm Hg measured in the supine position.

If a subject is withdrawn from study treatment due to an AE or a SAE, the subject will be followed up by the investigator until the abnormal parameter or symptom has resolved or stabilized (if applicable). Additional clinical work-up to further evaluate an AE or SAE may be recommended by the site investigator, in conjunction with the Medical Monitor, and the subject's treating ALS physician. It is recommended that the investigator consult with the Medical Monitor prior to removing the subject from study treatment for any reason except subject withdrawal of consent. Any subject may withdraw his or her consent at any time for any reason.

For all research subjects, the reason for permanent discontinuation of study drug must be recorded in the electronic eCRF. These data will be included in the trial database and reported.

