8.5. Assessment of Adverse Events

8.5.1. Assessment of Adverse Event/Serious Adverse Event Severity

The severity, or intensity, of an AE refers to the extent to which an AE affects the subject’s daily activities. Severity will be graded according to the World Health Organization (WHO) Toxicity Grading Scale, March 2020 or later. If an AE is not specified within the WHO Toxicity Grading Scale, then the AE will be graded according to the following definitions:

Grade	Severity	Description
1	Mild	Transient or mild discomfort; no limitation in activity; no medical intervention or therapy required. The subject may be aware of the sign or symptom but tolerates it reasonably well.
2	Moderate	Mild to moderate limitation in activity; no or minimal medical intervention or therapy required.
3	Severe*	Marked limitation in activity; medical intervention or therapy required; hospitalizations possible.
4	Life-Threatening	The subject is at risk of death due to the AE as it occurred. This does not refer to an AE that hypothetically might have caused death if it were more severe.
5	Death	Any AE where the outcome is death.

Abbreviation: AE=adverse event.

*Note that the term “severe” is a measure of intensity and that a severe AE is not necessarily serious.

Changes in the severity of an AE should be documented to allow an assessment of the duration of the event at each level of intensity to be performed. AEs characterized as intermittent do not require documentation of onset and duration of each episode. When the intensity of an AE changes more than once a day, the maximum severity for the event should be listed. If the intensity changes over a number of days, these changes should be recorded separately (ie, as having distinct onset dates).

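### Table 1 of the protocol both forbids and allows further dosing after a nonserious Grade 3 infusion reaction; its Grade 1 row also does not match its own criterion

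*Protocol*

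**What the plan says.** Table 1 in Protocol Section 5.8.1 gives, for each grade of acute infusion reaction, a criterion, a treatment instruction and a rule for later doses. Grades 3 and 4 share one row.

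- The Treatment cell of that row ends: "Subject is permanently discontinued from further trial treatment administration".
- The cell for subsequent dosing in the same row says first: "Any subject with a serious Grade 3 or any Grade 4 event will not be permitted to re-dose". It then adds: "Any subsequent redosing of nonserious Grade 3 events must be discussed and approved with the Medical Monitor".

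Protocol Section 8.5.1 separates severity from seriousness, noting that "a severe AE is not necessarily serious".

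Protocol Section 6.1 introduces its entries with "The following is a list of possible reasons for study drug discontinuation". Item 11 of that list includes a reaction occurring "despite adequate pre-medication for an initial occurrence of a moderate to severe infusion related reaction".

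For Grade 1, the Table 1 criterion reads "Mild transient reaction; infusion interruption not indicated; intervention not indicated", and the action beside it reads "Stop infusion and monitor symptoms. If symptoms resolve without intervention, the infusion may be restarted at 50% of the original infusion rate".

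**The concern.** A permanently discontinued subject cannot be redosed, whoever approves it. If the Treatment cell applies to everyone in the row, the sentence about redosing after nonserious Grade 3 reactions has no subjects to apply to. If that sentence has effect, the Treatment cell is wrong for those subjects.

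The first consequence concerns safety. One site may stop treatment for good under the Treatment cell, while another asks the Medical Monitor to approve another dose after the same kind of reaction.

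The second concerns compliance. The same redosing follows one cell and breaches the other. Protocol Section 10.7 rules out prospective waivers, and SAP Section 4.3 lists important deviations, a category that includes those affecting subject safety. It should therefore be clear which conduct is within protocol.

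The third concerns a primary endpoint. Tolerability (Protocol Section 9.3.6.2) depends on completing the trial with no treatment-emergent adverse event that ends treatment, so the cell a site follows can decide how a subject is counted.

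**Working it through.** The plan gives no figure on this point to reproduce. The main check sets the texts side by side; the arithmetic only bounds the effect on tolerability.

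**1. What each cell of the Grades 3 or 4 row requires**

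| Reaction | Treatment cell | Subsequent-dosing cell | Agree? |
|---|---|---|---|
| Grade 4 | no further dosing | no further dosing | yes |
| Grade 3, serious | no further dosing | no further dosing | yes |
| Grade 3, nonserious | no further dosing | dosing possible if the Medical Monitor approves | no |

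**2. Whether the disputed class can occur.** It can. The Grade 3 criterion in Table 1 covers prolonged reactions and symptoms that return after improving, as well as reactions needing hospital care. The first two need not meet any seriousness criterion in Section 8.2. Section 8.5.1 says that severe does not imply serious, and the subsequent-dosing cell itself names nonserious Grade 3.

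**3. Whether other text settles it.** None does.

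- Section 6.1 lists possible reasons for discontinuation, not a rule for this case. As worded, item 11 covers pre-medication after a first reaction that was moderate *to severe*. It therefore contemplates dosing after a severe first reaction, which does not fit an unconditional stop.
- The amendment summary entry for Section 5.8.1 concerns laboratory sampling only.
- The SAP contains no rule on dosing after infusion reactions.

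**4. Grade 1.** The criterion says interruption is not indicated; the action is to stop the infusion. An indicated interruption is part of the Grade 2 criterion, together with a prompt response to treatment of symptoms. Following the Grade 1 action therefore blurs the line between the two grades.

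**5. Size under the planned tolerability analysis.** Protocol Section 9.1 gives 45 subjects randomized 2:1, with 30 exposed to AL001. Take one AL001 subject with a nonserious Grade 3 reaction:

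- Under the Treatment cell, the subject stops because of the event and counts as a failure.
- Under the other cell, the subject counts as a success only if redosing is approved and the subject completes without a further treatment-emergent event leading to discontinuation. Otherwise the subject is a failure under both cells.

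The change per subject is therefore either 0 or 1/30 = 3.3 percentage points.

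As an illustration, assume one such subject, no other failures, and two-sided 95% Clopper-Pearson limits. The level is an assumption, since the protocol specifies exact bounds without one.

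- 30/30 = 100%. Lower limit = 0.025^(1/30) = 0.884, so the interval is 88.4% to 100%.
- 29/30 = 96.7%. The lower limit solves 30p^29(1 − p) + p^30 = 0.025, giving p = 0.828. The upper limit solves p^30 = 0.975, giving p = 0.999. The interval is 82.8% to 99.9%.

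The documents give no rate of infusion reactions, so no expected number of affected subjects can be stated.

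**The case against.** **Default with exception.** The two columns answer different questions, one about the event and one about later doses. The row could be read as a default stop with an exception controlled by the Medical Monitor. This is the most favourable reading, but no word such as *unless* links the cells. The Grade 2 row, by contrast, does state the condition on which it discontinues a subject permanently. It is true that no site may redose on its own, and that Section 6.1 recommends consulting the Medical Monitor before taking a subject off treatment. That narrows the scope for divergence. It does not remove it, because the consultation is only recommended and a site following the Treatment cell has no reason to ask for redosing.

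**Guidance only.** The section and table are titled as guidance, and redosing under an express sentence of the protocol might never be recorded as a deviation. That may be so in practice. The row's wording is mandatory in both cells, however, and the text does not say which prevails.

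**Item 11.** Grade 2 reactions already give its reference to pre-medication some content, and the grade definitions in Section 8.5.1 apply only where the WHO scale is silent. Item 11 is therefore supporting evidence. It still names severe first reactions and belongs in the reconciliation. The contradiction within the row does not depend on it.

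**Grade 1.** An action more cautious than the grading criterion can be carried out, and the treatment cell for every grade begins by stopping the infusion. The mismatch is on the page, but it is rightly secondary.

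**The analysis will not be run.** The SAP reports that the study was halted with five participants, not for safety reasons, and plans listings only. That stands, and it limits the present effect. The dosing rule also applies to placebo subjects under the blind, where the planned arm is 45 − 30 = 15 and one subject is 1/15 = 6.7 points.

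**Conclusion.** The concern holds. The Grades 3 or 4 row contradicts itself for nonserious Grade 3 reactions and only for those, and nothing else in the protocol or SAP resolves it. This is an internal contradiction in a stopping rule that bears on patient safety, and it should be fixed. The Grade 1 mismatch is real but secondary.

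The effect on the planned AL001 tolerability percentage is 0 to 3.3 points per affected subject, given the planned arm of 30. The upper figure requires approved redosing followed by completion. The interval illustration assumes one affected subject, no other failures and a 95% level. For the synoptic report the effect is confined to interpreting the adverse event, discontinuation, exposure and deviation listings. The documents do not say whether any such reaction occurred.

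**What to change.** Reconcile the two cells of the Grades 3 or 4 row and Section 6.1 item 11 into one consistent statement on nonserious Grade 3 reactions. Reconcile the Grade 1 criterion with the Grade 1 action. Which clinical rule should apply is the sponsor's decision.

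For the synoptic report, if any nonserious Grade 3 infusion reaction occurred, say which cell was applied when the discontinuation or any deviation was classified.

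The cost is a wording change in one table row, one list item and one Grade 1 cell, and at most one sentence in the report. No new data or SAP listing is required.

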6. STUDY DRUG DISCONTINUATION AND SUBJECT WITHDRAWAL FROM THE STUDY

6.1. Study Drug Discontinuation

An investigator may discontinue study drug or a subject may also choose to discontinue study drug at any time. Subjects who plan to discontinue early from the study drug or study should complete an Early Termination Visit 8 weeks after the last dose of study treatment.

The following is a list of possible reasons for study drug discontinuation:

1. Subject is noncompliant with the protocol
2. Subject is lost to follow-up
3. Subject withdraws consent
4. Subject has a serious or intolerable AE that, in the opinion of the investigator, requires withdrawal from the study treatment
5. Occurrence of an intercurrent illness that, in the opinion of the investigator, will affect assessments of clinical status or safety to a significant degree
6. Use of a nonpermitted concomitant medication
7. Pregnancy
8. Discretion of the investigator and Medical Monitor
9. Serum transaminases (ALT or AST) $>3 \times$ ULN and total bilirubin $>2 \times$ ULN without an alternative explanation
10. Anaphylaxis
11. Infusion-related or injection-related reaction despite adequate pre-medication for an initial occurrence of a moderate to severe infusion related reaction or if the subject experiences any of the following events: mucosal tissue involvement, airway compromise, or symptomatic hypotension with systolic BP <90 mm Hg measured in the supine position.

If a subject is withdrawn from study treatment due to an AE or a SAE, the subject will be followed up by the investigator until the abnormal parameter or symptom has resolved or stabilized (if applicable). Additional clinical work-up to further evaluate an AE or SAE may be recommended by the site investigator, in conjunction with the Medical Monitor, and the subject's treating ALS physician. It is recommended that the investigator consult with the Medical Monitor prior to removing the subject from study treatment for any reason except subject withdrawal of consent. Any subject may withdraw his or her consent at any time for any reason.

For all research subjects, the reason for permanent discontinuation of study drug must be recorded in the electronic eCRF. These data will be included in the trial database and reported.

6.2. Subject Withdrawal from the Study

Subjects may withdraw from the study at any time for any reason. An investigator should only withdraw a subject from the study if required to ensure the subject's safety even after discontinuation of study drug. The following is a list of possible reasons for subject withdrawal from the study:

1. Subject withdraws of consent
2. Subject is lost to follow-up
3. Subject is withdrawn from the study at the discretion of the investigator
4. Subject is withdrawn due to administrative or other reasons (eg, termination of the study by Alector)

All subjects who discontinue the study during and after the treatment phase, but before the final scheduled Study Completion Visit should be encouraged to return to the investigational site for an Early Termination Visit 8 weeks after the last dose of study treatment.

Reasonable attempts will be made by the investigator to obtain reasons for subject withdrawal (eg, 2 documented telephone calls on different days, followed by 1 registered letter). The reason for subject withdrawal from the study will be recorded on the eCRF.

6.3. Subject Lost to Follow-Up

A subject will be considered lost to follow-up if he or she fails to return for 3 consecutive scheduled study visits and is unable to be contacted by the study site staff.

The following actions must be taken and documented if a subject fails to return to the clinic for a required study visit:

- The site will attempt to contact the subject and reschedule the missed visit within the study window and counsel the subject on the importance of maintaining the assigned visit schedule and ascertain if the subject wishes to continue or should continue in the study.
- Before a subject is deemed lost to follow-up, the investigator or designee will make every effort to regain contact with the subject (where possible, 3 telephone calls and if necessary, a certified letter to the subject's last known mailing address or local equivalent methods). These contact attempts should be documented in the subject's medical record or study file.
- Should the subject continue to be unreachable, he or she will be considered to have withdrawn from the study with a primary reason of "lost to follow-up".

7. STUDY ASSESSMENTS AND PROCEDURES

7.1. Efficacy Assessments

7.1.1. ALS Functional Rating Scale-Revised

The ALSFRS-R is a quickly administered (5-minute) ordinal rating scale used to determine the patient's assessment of their capability and independence in 12 functional activities ([Cedarbaum 1999](#)). All ALSFRS-R evaluators must be certified by the Northeast ALS Consortium (NEALS). Each functional activity is rated 0–4 for a total score that ranges from 0 to 48. Higher scores indicate better function. Initial validity in ALS patients was established by documenting that change in ALSFRS-R scores correlated with change in strength over time, was closely associated with quality-of-life measures, and predicted survival. The test-retest reliability is greater than 0.88 for all test items. The advantages of the ALSFRS-R are that all 12 functional activities are relevant to ALS, it is a sensitive and reliable tool for assessing activities of daily living function in those with ALS, and it is quickly administered. With appropriate training the ALSFRS-R can be administered with high inter-rater reliability and test-retest reliability.

When required due to pandemic-related restrictions, the ALSFRS-R can be administered via phone or web-based interface. The ALSFRS-R can be administered by phone with good inter-rater and test-retest reliability. The equivalency of phone versus in-person testing, and the equivalency of study subject versus caregiver responses have also been established. Additionally, the ALSFRS-R can also be obtained using a web-based interface with good concordance with in-person assessment.

7.1.2. Combined Assessment of Function and Survival

The Combined Assessment of Function and Survival (CAFS) ([Berry 2013](#)) evaluates treatment-dependent differences in disease progression as measured by survival time or change in function. CAFS ranks each pair of subjects' clinical outcomes based on survival time if evaluable or based on change in the ALSFRS-R total score if a comparison based on survival time is not evaluable. A subject's CAFS score is the sum of their ranking with respect to all other subjects. A higher CAFS score indicates a better outcome. CAFS scores are nonparametric and thus do not rely on statistical assumptions required for many of the standard techniques, such as linearity of disease progression or imputation of missing data.

